9.7 Statistical tests

For details, see the statistical section under 8.3.

9.8 Suspension of research

This is pilot study, but after periodic evaluation of study result and safety profile, the PI can terminate the research anytime based on outcomes of periodic safety monitoring and benefit/risk outcomes and will inform the IRB if such a decision is being made.

10.0 Risks

The following risks are associated with PGZ during study treatment

Hypoglycemia: PGZ along with sulfonyl urea, other oral diabetic agents or insulin can cause mild to moderate hypoglycemia when used in conjunction with insulin or an insulin secretagogue. Under these conditions a lower dose of the insulin or insulin secretagogue may be needed to reduce the risk of hypoglycemia. Therefore, finger sticks glucose measurements will be performed 2h after initial study drug administration (time of peak of PGZ concentration) and subsequently at regular time points as determined by the standard of care protocol for stroke patients (see attached standard of care protocols for hypoglycemia and hyperglycemia for acute stroke patients, **Appendix 1**).

Cold-like symptoms such as headache, sinus infection, muscle pain and sore throat.

Edema: Dose-related edema may occur following long-term treatment with PGZ. However in this acute study of 3 doses edema is unlikely to occur, would be temporary and not cause a risk to study subjects.

Liver dysfunction: Long-term PGZ treatment may cause liver dysfunction, nausea, vomiting, stomach pain, unusual or unexplained tiredness, loss of appetite, dark urine, or jaundice which is unlikely to occur during the short treatment duration in this study. However, patients with type 2 diabetes may have fatty liver disease or cardiac disease with episodic congestive heart failure, both of which may cause liver test abnormalities, and they may also have other forms of liver disease, many of which can be treated or managed. Therefore, liver tests (serum ALT, AST, and total bilirubin) will be assessed prior to initiating study drug treatment and 24 hours after the second dose of study drug has been administrated. If after the second dose of study administration the ALT and/or AST should raise to 2.5 times the upper limit of normal and/or total bilirubin > 1.2 mg/dl study treatment will be stopped and patients will continue to be monitored and treated as deemed appropriate by the treating physician.

Congestive heart failure: Fluid retention may occur and can exacerbate or lead to congestive heart failure. Combination use of PGZ with insulin and use in congestive heart failure NYHA Class I and II may increase the risk. Although this is unlikely to occur during the brief treatment duration in this study, patients will be closely monitored for signs and symptoms of an acute exacerbation of congestive heart failure. If this should occur, treatment with the study drug will be stopped and patients will continue to be monitored and treated as deemed appropriate by the treating physician.

Bladder cancer: Long term use of PGZ may increase the risk of bladder cancer. Patients with active bladder cancer or history of bladder cancer will therefore not be included in this study.

Risk of randomization: The active research treatment may prove to be more/less effective or have more side effects than the placebo research treatment.

During blood draws, discomfort associated with the insertion of a needle into a vein is a slight pinch or pinprick when the sterile needle enters the skin. The risks of a blood draw include mild discomfort and/or a black and

blue mark at the site of puncture. Less common risks include a small blood clot, infection, or bleeding at the puncture site, and on rare occasions fainting during the procedure.

Loss of confidentiality is always a risk, but every attempt will be made to prevent any loss of data and to protect our patients' information, maintaining privacy, and keeping all data in a de-identified and password protected storage area.

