- Time of symptom onset or last known well time
- Current medication usage
- Results from the standard care laboratory workup including complete blood count, coagulation studies, basic metabolic panel (including serum glucose, renal function, and electrolytes), and if applicable results of pregnancy test and urinary drug screen)
- Health care services rendered (diagnostic workup procedures, use of t-PA, and thrombectomy, use of antibiotics, treatment of cerebral edema and hemorrhagic conversion)
- Images and results of the interpretation of the neuroimaging studies (brain MRI and head CT)
- NIHSS and mRS scale

The following assessments will be **performed only for research**:

- BI, GOS will assess neurological outcomes and will be performed by certified study personnel.
- MOCA will assess cognitive function and will be performed by certified study personnel.
- Blood will be collected (approximately 15 mls.) for the following tests:
 - ESR, hsCRP, CBC with differential, blood glucose, insulin, cortisol and catecholamines
 - T Cells, B cells, activated myelocytes
 - Inflammatory markers, cytokines, apoptotic markers
 - Other biomarkers.
 - AST, ALT and total bilirubin

4. Administration of the Investigational Product: Study treatment administration will be initiated within 18 hours after the onset of stroke symptoms or last known well time. Liver function tests (serum ALT, AST, and total bilirubin) will be assessed prior to initiating study drug treatment. The treatment group will receive a 45 mg Pioglitazone capsule orally every 24 hours for 3 days for a total of 3 doses. The control group will receive placebo at the same time points. Both groups will be treated identically and receive best standard of care.

If subject will be unable to swallow the study drug, will be administered via feeding tube (See study drug detailed in sections 7.4.2 and 7.4.5).

In addition, for research purposes finger stick glucose measurements will be performed 2h after initial study drug administration (time of peak of PGZ concentration) and subsequently at regular time points as determined by the standard of care protocol for stroke patients (see attached standard of care protocols for hypoglycemia and hyperglycemia for acute stroke patients, Appendix 1).

7.2. 2 Day 1

This will occur 24 (+/- 2) hours after the initial dose of the investigational product is administered. At this time, the following **research-only activities** will occur:

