- AEs and concomitant medications will be documented.
- Prior to administration of the investigational product, blood will be collected (approximately 10 mls) for the following tests: ESR, hsCRP, CBC with differential, blood

glucose, insulin, cortisol and catecholamines, T Cells, B cells, activated myelocytes, inflammatory markers, cytokines, apoptotic markers, other biomarkers.

- The second dose of investigational product will be administered.

7.2. 3 Day 2

This will occur 24 (+/- 2) hours after the second dose of investigational product is administered.

At this time, the following **research-only activities** will occur:

- AEs and concomitant medications will be documented.
- Prior to administration of the investigational product, blood will be collected (approximately 10 mls) for the following tests: ESR, hsCRP, CBC with differential, blood glucose, insulin, cortisol and catecholamines, T Cells, B cells, activated myelocytes, inflammatory markers, cytokines, apoptotic markers, other biomarkers.
- Prior to administration of the investigational product, blood will be collected (approximately 5 mls) and sent for liver function testing (AST, ALT and total bilirubin). Liver function test results will be confirmed prior to the administration of the investigational product.
- The third dose of investigational product will be administered.

7.2. 4 Day 3

This will occur 24 (+/- 2) hours after the third dose of investigational product is administered.

This may occur at the discharge visit, if that occurs prior to the scheduled day 3 visit. At this time, the following **research-only activities** will occur:

- AEs and concomitant medications will be documented.
- Blood collection (approximately 10 mls) for the following tests: ESR, hsCRP, CBC with differential, blood glucose, insulin, cortisol and catecholamines, T Cells, B cells, activated myelocytes, inflammatory markers, cytokines, apoptotic markers, other biomarkers.

7.2. 5 Discharge

This will occur on the day of discharge from the hospital. A standard of care routine physical and neurological examination will be conducted. The following assessments will be performed;

- NIHSS and mRS scale
- BI, GOS (for research only)
- MOCA (for research only)
- AEs and concomitant medications will be documented for **research-only**.

7.2. 6 Day 90 Visit

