This visit will occur 90 days (+/- 30 days) from the day of discharge. A standard of care routine physical and neurological examination will be conducted. If the patient is unable to travel to the clinic, the following assessments may be done via phone call:

- NIHSS and mRS scale
- BI, GOS (for research only)
- MOCA (for research only)
- AEs and concomitant medications will be documented for **research-only**.

Schedule of Study Activities

	Baseline (0-18h from symptom onset)	Day 1: 24+/-2h after first dose of study drug/ placebo 24 hrs	Day 2: 24+/-2h after second dose of study drug/ placebo	Day 3: 24+/-2h after third dose of study drug/ placebo	Discharge	Day 90: ± 30 days follow-up visit

Screening/Enrollment	X					
Informed consent	X					
Administration of study drug or placebo	X	X	X			
Clinical scales: NIHSS, mRS, BI, GOS, MOCA	X				X	X
Blood for laboratory tests and biomarkers	X (pre-treatment)	X (pre-treatment)	X (pre-treatment)	X		
Liver function test	X (pre-treatment)		X (pre-treatment)			
Medical history	X (pre-treatment)					
Physical and neurological examination	X (pre-treatment)				X	X
AEs and concomitant Medications		X	X	X	X	X
Blood glucose assessment via finger stick	X*					

BI = Barthel Index; GOS = Glasgow Outcome Scale; MOCA = Montreal Cognitive Assessment; mRS = modified Rankin Scale; NIHSS = NIH Stroke Scale

*finger stick glucose measurements will be performed 2h after initial study drug administration (time of peak of PGZ concentration) and subsequently at regular time points as determined by the standard of care protocol for stroke patients (see attached standard of care protocols for hypoglycemia and hyperglycemia for acute stroke patients, Appendix 1).

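### Minor, cheap improvement: no scheduled liver test follows the third dose, and the existing Day 3 draw could carry one

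*Combined protocol and SAP*

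**What the plan says.** Treatment is one 45 mg capsule every 24 h for three doses (7.2.1, item 4). Liver tests are placed as follows.

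- **Baseline (7.2.1):** "Liver function tests (serum ALT, AST, and total bilirubin) will be assessed prior to initiating study drug treatment".
- **Day 2 (7.2.3):** a sample of about 5 ml is taken 24 (+/- 2) h after dose 2 and before dose 3. "Liver function test results will be confirmed prior to the administration of the investigational product".
- **Day 3 (7.2.4):** "This will occur 24 (+/- 2) hours after the third dose of investigational product is administered". About 10 ml is drawn for blood counts, hormones, inflammatory markers and other biomarkers. ALT, AST and bilirubin are not listed. The timing can be earlier: "This may occur at the discharge visit, if that occurs prior to the scheduled day 3 visit".
- **Schedule table (7.2):** the row "Liver function test" is marked at Baseline and Day 2 only.
- **Risks (10.0):** the same two time points, in that the panel "will be assessed prior to initiating study drug treatment and 24 hours after the second dose of study drug has been administrated". Liver dysfunction is linked to long-term use, "which is unlikely to occur during the short treatment duration in this study". Testing is still required because these patients may have fatty liver, cardiac or other liver disease.

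The routine results taken from the record at baseline are a "standard care laboratory workup including complete blood count, coagulation studies, basic metabolic panel (including serum glucose, renal function, and electrolytes", and no liver enzyme is named there.

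On use of the results, 9.2 lists liver tests among the data to be reviewed. Section 18.7 stops treatment if AST or ALT exceeds 2.5 times the upper limit of normal or total bilirubin exceeds 1.2 mg/dl.

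**The concern.** Section 7.1 states that the safety of acute PGZ treatment will be established, and the regimen under study is three doses. Adverse events are recorded up to 24 h after the last dose (9.1), which is the Day 3 time point. The scheduled liver data stop one dose earlier, although blood is drawn at Day 3 anyway.

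The reason that 10.0 gives for testing, possible pre-existing liver or cardiac disease, does not end at dose 2. Section 7.4.2 adds that total PGZ concentrations are still raised 24 h after a once-daily dose, so a Day 3 sample would still reflect exposure.

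Two modest things are at stake. A symptom-free rise that first appears after dose 3 would not be picked up by any scheduled test. And if the multi-center trial foreseen in 2.3 keeps this regimen, it would start without scheduled liver data on the whole course.

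**Working it through.** The plan gives no figure on this point to reproduce. The check is a count of time points, doses, blood and panels, plus what 25 patients can show.

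**Timing, in hours from dose 1** (7.2.1 to 7.2.4; each step 24 +/- 2 h)

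- Dose 2: 24 +/- 2, so 22 to 26 h.
- Day 2 liver test, before dose 3: 48 +/- 4, so 44 to 52 h.
- Day 3 draw: 72 +/- 6, so 66 to 78 h, or earlier if taken at an early discharge.

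**Exposure covered by scheduled on-treatment liver tests**

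- Now: 2 of 3 doses, 2 x 45 = 90 mg of 3 x 45 = 135 mg, or 67%.
- With a Day 3 panel: 3 of 3 doses, 135 mg.
- Patients with a scheduled liver test after dose 3: 0 of 50 now (0 of 25 on PGZ; arm size from 8.2).

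**Blood and panels**

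- Research blood now: 15 (baseline) + 10 (Day 1) + 10 + 5 (Day 2) + 10 (Day 3) = 50 ml.
- With the panel, at the 5 ml used on Day 2: 50 + 5 = 55 ml, or 10% more.
- Panels: 2 x 50 = 100 now; at most 3 x 50 = 150 with the change.

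**What zero abnormal values would show**

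The one-sided 95% upper bound with zero events in n patients is 1 - 0.05^(1/n). For n = 25 it is 1 - 0.05^(1/25) = 11.3%. The bound is the same at Day 2 (after two doses) and at Day 3 (after three, if all 25 are sampled).

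**Chance that the added test shows something new**

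Only rises that first appear after the Day 2 sample count, because a rise already present then is caught by the existing test. Let p be the share of PGZ patients whose rise first appears between the two draws. The chance of at least one among 25 is 1 - (1 - p)^25. The documents give no value for p, so these rates are assumptions:

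| Assumed p | Chance of at least one in 25 |
|---|---|
| 1% | 22% |
| 2% | 40% |
| 5% | 72% |
| 10% | 93% |

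The definition of p matters. If 2% of patients had a rise at Day 3 and half of those rises were already visible at Day 2, p would be 1% and the added chance 1 - 0.99^25 = 22%, not 40%.

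**The case against.** The strongest reply is that nothing is broken. The text, the table and 10.0 agree, and the plan gives its reasoning: liver harm is expected with long-term use, patients are tested before exposure and again before the last dose, and treatment stops on an abnormal result. After dose 3 there is no dose left for the rule in 18.7 to act on. Liver outcomes are not among the objectives or endpoints in section 1.0, and the Day 2 test already gives 9.2 something to review. Adverse events are documented at Day 3, discharge and Day 90, so symptomatic harm has a route to detection.

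All of that stands, and it is why this is an improvement and not an error. It does not remove the gap in scheduled data after the complete course.

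Two practical objections also stand. First, 7.4.5 and 12.0 keep study laboratory results from treating physicians, so a Day 3 panel without a stated reporting route might help no patient. Second, 7.2.3 lists the liver sample as a separate collection, so sparing the patient another needle stick depends on taking the tube at the same venipuncture.

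A reader might infer that dose 3 is given without liver monitoring. The documents say the opposite, since the Day 2 result must be confirmed first. A reader might also infer that a rise after dose 3 would go unseen altogether. That too goes too far: a treating physician may order a test, documented abnormal findings are reviewed (18.3), and those believed to be drug-associated are followed (18.2). These sections act on findings once they exist; they do not schedule a test.

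**Conclusion.** The point holds as a minor, inexpensive improvement. Scheduled on-treatment liver data cover two of three doses, and none of the 50 patients has a scheduled value after the full course. No endpoint and no dosing decision changes.

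The benefit is confined to rises that first appear between about 48 h and 72 h. Its size is unknown, because the documents give no rate. The 22% to 93% range applies only to assumed rates of 1% to 10% for such new rises, with all 25 PGZ patients sampled. Patients stopped at Day 2 would not receive dose 3, and a draw at an early discharge reflects that dose only in part, so the real yield would be lower.

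It would be wrong to read the added test as establishing hepatic safety. With at most 25 PGZ patients, zero abnormal values still allow a rate of up to 11.3%, and a rise appearing after Day 3 would still be missed.

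**What to change.** Keep the Day 2 test as the check before dose 3, and then:

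- Add AST, ALT and total bilirubin to the existing Day 3 draw, or to that draw when it is taken at discharge. Change 7.2.4, the schedule table and 10.0 to match.
- Record the hours since the last dose with each Day 3 sample.
- State that a Day 3 value above the existing limits (2.5 times the upper limit of normal for AST or ALT, or bilirubin above 1.2 mg/dl) goes to the treating physician and the safety monitor, with review and follow-up under 18.3 and 18.2. Make this an explicit exception to 7.4.5 and 12.0.

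The cost is about 5 ml more blood per patient (about 50 to about 55 ml) and at most 50 more panels. There is no new visit, and no extra needle stick if the tube is taken at the same venipuncture. Dosing rules and thresholds stay as they are.

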11.0 Potential Benefits to Subjects and Others

11.1 Potential Benefits to Subjects

Subjects may or may not benefit from participation in this study. It is unclear whether PGZ treatment will lead to any benefits in study subjects as no data are currently available. However, possible benefits the subject may experience from this research study include the possible reduction of infection, which may reduce the brain injury following stroke, and a feeling of improvement of short and long term symptoms and day-to-day function.

11.2 Potential Benefits to Others

The potential benefit to society and others includes increasing knowledge regarding the effects of PGZ on clinical outcomes and its effect on the stress-immune response in acute hyperglycemic patients. New knowledge gained from this study could give way to novel treatments to help stroke recovery for a high-risk population.

12.0 Sharing Results with Subjects

Study results of individual subjects result will not be shared with subjects, the LAR or any treating physician.

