3.2 Exclusion Criteria

Patients will be excluded from study entry if any of the following exclusion criteria exist at screening:

1. Known hypersensitivity to PGZ.
2. Infection at the time of presentation as defined by body temperature $> 38^{\circ}\text{C}$, pneumonia evident on chest X-ray, urinary tract infection (positive tests for nitrites, leukocyte esterase, and bacteria on urine analysis), other acute infection per history or current use of antibiotic or antiviral treatment.
3. Active malignancy and / or autoimmune disease requiring treatment.
4. Use of immunomodulatory drugs or chemotherapy.
5. History of stroke or brain injury within the last 90 days prior to presentation.
6. Acute illness within the last 30 days which could have affected the white blood cell count.
7. Known history of clinically significant hypoglycemia.
8. Patients already taking PGZ.
9. Active liver disease (ALT and /or AST 2.5 times the upper limit of normal, total bilirubin > 1.2 mg/dl).
10. Acute decompensated heart failure, and/or admission for an acute coronary syndrome, myocardial infarction (MI), cardiac arrest, coronary artery surgery within the past 3 months and patients with New York Heart association Class III and IV heart failure.
11. History of bladder cancer
12. Pregnant and nursing women.
13. Currently incarcerated patients.

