Participants will be randomized to either PGZ or placebo using an equal allocation ratio (1:1). The randomization will be performed using a random number generator via the PLAN procedure within SAS software, version 9.4 (SAS Institute Inc., Cary, NC). Personnel in the Department of Public Health Sciences (PHS) will use the PLAN procedure within SAS software to generate a randomization list using variable-size, random permuted blocks to ensure that the number of participants in each arm is balanced after each set of B randomized participants, where B is the block size. Personnel in PHS will choose the block sizes without revealing it to any of the investigators or study personnel who will be collecting and reviewing outcomes data. The PHS generated randomization list will be provided to Investigational Drug Services (IDS) who will be implementing the randomization for this trial.

7.4. 4 Subject Compliance Monitoring

Nursing staff will chart administration of study drug into the patient's EMR and study personnel will monitor and document the completion of all study procedures.

7.4. 5 Blinding of the Test Article

The investigators, study staff, subjects, and caregivers will be blinded to the subject's treatment assignments for the duration of the trial. Investigational pharmacy will be placed the investigational product into a plain capsule to insure that the investigative team remains blinded (see Section 7.4.6.3). To avoid unblinding of the study team members, if the capsules have to be

opened/crushed for administration by nursing staff, a warning label will be placed on study drug package telling the bedside nurse not to reveal the contents of the capsule to any study team member. Study team members will not administer any study drug.

All blood samples will be coded to maintain masking prior to analysis. The laboratory staff will be unaware of the condition and the treatment of the participants for whom they will conduct the assays as the samples will be identified only with a study number.

The results of the laboratory measurements will not be shared with the treating physicians, and will not impact patient care.

7.4. 6 Receiving, Storage, Dispensing and Return

7.4 .6.1 Receipt of Test Article

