9.0 Data and Safety Monitoring Plan

9.1 Periodic evaluation of data

To monitor safety throughout the course of the study, every effort will be made to remain alert to possible AEs/SAEs. If an AE/SAE occurs, the first concern should be for the safety of the subject. If necessary, appropriate medical intervention will be provided. At the signing of the written consent form, each subject or his/her legally authorized representative and/or main caregiver must be given the names and telephone numbers of study site staff for reporting AEs/SAEs and medical emergencies.

As recommended by NCATS, our study team has identified an independent safety monitor for our study. [name] (endocrinologist) has kindly agreed to serve in this role. She will review every adverse event during the study (as described in the next paragraph) based on severity and relationship to the study treatment. She will also review patient safety regularly after every 10th patient enrollment.

In this study, any AE/SAE experienced by the subject between the time of first dose of study treatment and 24 hours after the last dose will be recorded on the electronic case report form, regardless of the severity of the event or its relationship to study treatment. During study treatment and visit after 90 days, the research team will assess the subject for AEs and will record any new AEs/SAEs or updates to previously reported AEs on the electronic case report form.

The data will be reviewed by the study statistician in the Public Health Science department. If our trial allows us to reach our predetermined alpha with fewer patients than our predicted sample size, than periodic evaluation will allow us to avoid randomizing patients to a treatment that is potentially inferior. The data will be reviewed once, when 50% of patients have been enrolled in each arm.

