18.3 Causality and Severity Assessments

The investigator will promptly review documented adverse events and abnormal test findings to determine 1) if the abnormal test finding should be classified as an adverse event; 2) if there is a reasonable possibility that the adverse event was caused by the study drug(s) or device(s); and 3) if the adverse event meets the criteria for a serious adverse event.

If the investigator’s final determination of causality is “unknown and of questionable relationship to the study drug(s) or device(s)”, the adverse event will be classified as associated with the use of the study drug(s) or device(s) for reporting purposes. If the investigator’s final determination of causality is “unknown but not related to the study drug(s) or device(s)”, this determination and the rationale for the determination will be documented in the respective subject’s case history.

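### Sections 12.0 and 7.4.5 bar study results from the treating physician with no exception for the Day 2 liver tests, yet 10.0 leaves a patient stopped for those tests in that physician's care

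*Combined protocol and SAP*

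**What the plan says.** Four parts of the protocol bear on this.

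- **12.0 Sharing Results with Subjects:** "Study results of individual subjects result will not be shared with subjects, the LAR or any treating physician". This is the whole section; it has no exception.
- **7.4.5 Blinding of the Test Article:** "The results of the laboratory measurements will not be shared with the treating physicians, and will not impact patient care". This follows sentences on coded samples and masked laboratory staff, but is not itself limited to those assays.
- **7.2.1 and 7.2.3:** AST, ALT and total bilirubin at baseline are among the assessments done only for research. The Day 2 panel, a separate draw of about 5 ml before dose 3, is among that day's research-only activities. For Day 2 the protocol adds: "Liver function test results will be confirmed prior to the administration of the investigational product". It does not say who receives the result.
- **10.0 Risks, liver dysfunction:** if, after the second dose, ALT and/or AST reach 2.5 times the upper limit of normal and/or bilirubin exceeds 1.2 mg/dl, "study treatment will be stopped and patients will continue to be monitored and treated as deemed appropriate by the treating physician". Section 18.7 repeats the stop but has no notification step.

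**The concern.** The two rules pull against each other. One withholds individual study results from every treating physician. The other relies on the treating physician's judgment after a study result has crossed a safety threshold. Staff who follow 12.0 to the letter have an explicit bar on passing on the liver value and no explicit permission to do so.

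The liver value is also the kind of finding a clinician may not notice unaided. 10.0 treats heart failure with the same stop-and-hand-over formula, but there the trigger is signs and symptoms that the treating team can see at the bedside. A raised transaminase may have none. What is at stake is the care of the individual patient; no estimate or test is affected.

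**Working it through.** The plan states no figure here, so the check compares the sections and then counts the panels that could be involved.

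**1. Are the liver tests covered by the bar?** 12.0 covers the study results of individual subjects. 7.2.1 and 7.2.3 class the liver tests as research-only, so they fall within its plain words. 7.4.5 is less certain. Its context, the separate liver draw and the separate row in the schedule of activities all suggest that it was meant for the coded assays. It also says the results will not affect care, which cannot be true of a test that decides whether dose 3 is given. As worded, though, it has no limit.

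**2. Does the treating physician need the value?** Under 10.0 the threshold stops study drug, and monitoring and treatment then follow that physician's judgment.

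**3. Does any other section release the value?**

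| Section | What it provides | Names the treating physician as recipient? |
|---|---|---|
| 7.4.4 | Dosing charted in the EMR | No; shows that dose 3 was not given, and is not said to show why |
| 9.1 | "If necessary, appropriate medical intervention will be provided" | No |
| 9.2 | Review of liver tests under the monitoring plan | No |
| 18.2 | Follow-up of drug-associated abnormal findings until acceptable to the investigator | No |
| 18.3 | "The investigator will promptly review documented adverse events and abnormal test findings" | No |
| 18.7 | Discontinuation at the liver thresholds | No |

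The standard-care laboratory list in 7.2.1 does not name liver tests. It is not exhaustive, so the treating team may have its own results, but 10.0 does not rely on that.

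**4. How many panels could trigger the conflict?** Inputs: 50 patients (8.1) and two scheduled liver panels each, at baseline and Day 2 (schedule in 7.2).

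- All scheduled panels: 50 × 2 = 100.
- Baseline panels: 50 × 1 = 50. These cannot lead to the 10.0 hand-over, which applies only after the second dose. Values over the thresholds at baseline are an exclusion under 3.2 item 9.
- Day 2 panels: 100 − 50 = 50 at most, one per patient.

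Section 3.3.2 allows withdrawn subjects to be replaced, which could raise the count slightly. The documents give no rate of threshold crossing, and none is assumed.

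**The case against.** The best defense is that this is a strained literal reading. 7.4.5 belongs to blinding and is evidently about masked assays. 12.0 sits among administrative sections and reads as a general statement on returning results. The specific safety text in 10.0 and 18.7 would ordinarily prevail, and 10.0 presupposes that the physician knows why drug was stopped. Its wording also describes care that continues, not a transfer of the liver work-up away from the investigator, who keeps follow-up under 18.2 and review under 18.3. Investigator and treating physician may even be the same person, and the consent pages, which are not available here, might address disclosure.

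Much of this is reasonable. The point about 7.4.5 is probably right, and 18.2 means the patient is not left unmanaged. But 12.0 stands apart from any blinding context and names treating physicians expressly. That specific text overrides general text, or that the two roles coincide, is inference; the protocol says neither. None of the sections relied on names the treating physician as a recipient or sets 12.0 aside. The unseen consent pages remain a limit on the claim that no route exists, but wording there would still leave 12.0 needing correction.

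**Conclusion.** The concern holds, as a minor conflict in the protocol as written. A rule stated without exception would, if followed literally, keep a safety result from the clinician responsible for the patient's care.

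Its reach is at most one Day 2 panel per patient. The conclusion rests on 12.0 meaning what it says and on the liver tests counting as study results, as their research-only label implies. It does not show that results would in practice be withheld: the treating team could learn them from the investigator or from its own tests. Confidence is medium for that reason.

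**What to change.** Add one sentence to each of 7.4.5 and 12.0:

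- In both sections, limit non-disclosure to the coded exploratory biomarker assays.
- State that liver results meeting the 10.0 or 18.7 thresholds are reported promptly to the investigator and the treating physician, without treatment assignment.

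The same exception could sensibly cover the 2-hour research finger-stick glucose, since 18.7 relies on the treating team to correct hypoglycemia.

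The cost is a text amendment. No test or visit is added, and masking of treatment assignment and of the exploratory biomarkers is unchanged.
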